4.1 Enrolment/screening period

4.1.1 Enrolment (Visit 1) Day -35

Each potential patient will provide written informed consent prior to any study specific procedures and undergo assessments applicable for the visit (see [Table 2](#)).

Demographics data collected will include date of birth/age, sex, race and ethnicity.

Patient must sign the Informed Consent Form (ICF) prior to any Visit 1 procedures and prior being instructed to withhold any medication. Registration of patient's enrolment via IWRS/IVRS should occur on the day of ICF signature.

Visit 1 assessments are primarily concerned with confirmation of the asthma disease state and the requisite level of severity based on background medications.

A record of physician-diagnosed asthma is required in source documentation prior to enrolment. A patient's verbal history suggestive of asthma symptoms, but without supporting documentation, is not sufficient to satisfy this inclusion criterion.

The following procedures are to be performed and/or data to be collected at Visit 1 (please refer to the schedule of assessments for details):

- Informed consent process
- Confirmation of eligibility criteria
- Height/Weight/BMI
- Complete physical examination
- Medical and asthma history (including prior medication use)
- A record of at least 2 asthma exacerbations within the previous 12 months must also be documented in source prior to enrolment
- ACQ-6 score must be ≥ 1.5 . If this criteria is not met the patient must be screen failed and will not be allowed to rescreen.
- ECG
- Vital signs
- Laboratory assessments (including clinical chemistry, hematology, urinalysis, serum pregnancy test, FSH (if needed) and serology for Hepatitis B, C, HIV-1, HIV-2)

- Reversibility testing - can be performed only in case the patient meets appropriate medication restrictions. If a patient has not met the required medication restrictions or fails the protocol-specified reversibility criterion ($\geq 12\%$ and 200 ml) at Visit 1, further attempts are allowed at Visit 2 or at Visit 3. If participating in the body plethysmography sub-study, the patient must meet reversibility criteria at Visit 1 or 2. No further attempt is allowed at Visit 3

4.1.2 Screening/run-in (Visit 2) Day -21

Assessments applicable for the period are listed in [Table 2](#).

Visit 2 is primarily concerned with evaluating whether lung function meets study eligibility criteria.

Ensure that the patient has met the required medication restrictions. Fractional exhaled NO measurements must be performed prior to any spirometry assessments.

Spirometry - Pre-bronchodilator FEV₁ criterion ($< 80\%$) will be tested for the first time at Visit 2. If reversibility testing was not performed at Visit 1 or a patient fails the protocol specified reversibility criterion ($\geq 12\%$ and 200 ml) a second attempt is allowed at Visit 2. For patients participating in the main study only - another attempt is allowed at Visit 3.

The following key procedures are to be performed and/or data to be collected on Visit 2 (please refer to the schedule of assessments for details):

- Revision of inclusion/exclusion criteria
- Collection of adverse events
- Concomitant medication review
- Vital signs measurement
- Fractional exhaled nitric oxide (FeNO) level measurement
- Pulmonary function tests (including Pre-BD FEV₁ testing, reversibility testing, if the reversibility criterion was not met at Visit 1).

4.1.3 Screening/run-in (Visit 3) Day -7

For main study only:

A pre BD FEV₁ should be recorded at Visit 2 as well as at Visit 3, irrespective of whether the patient has met protocol specified pre-bronchodilator FEV₁ criterion ($< 80\%$) at Visit 2 or not. If a patient fails the protocol specified reversibility criterion ($\geq 12\%$ and 200 ml) at Visit 1 or at Visit 2, a further attempt is allowed at Visit 3.

For sub study only:

Visit 3 is primarily concerned with body plethysmography assessments. Please ensure that all required medication restrictions are adhered to prior to performing these assessments.

A pre BD FEV₁ should be recorded at Visit 2 as well as at Visit 3, irrespective of whether the patient has met protocol specified pre-bronchodilator FEV₁ criterion (<80%) at Visit 2 or not. Please ensure that inclusion criteria #5 and #7 are met prior to performing body plethysmography assessments.

Reversibility testing cannot be performed at Visit 3. This criteria must be met at either Visit 1 or at Visit 2 for those patients participating in the sub-study.

4.1.4 Re-screening

If the reason for screen failure was transient (including but not limited to study-supplied equipment failure or unforeseen personal events that mandate missed screening visits), rescreening can be allowed only once.

Re-screened patient should re-sign informed consent on the re-screening Visit 1. All procedures from screening/run-in period should be repeated.

4.1.4.1 Procedures for patients who experience an exacerbation during screening/run-in

Patients who experience an asthma exacerbation during screening should be treated according to local medical practice. Once the exacerbation has been fully treated and the patient has returned back to their usual maintenance dose and remained on this dose for at least 2 weeks they can be rescreened (only once).

4.2 Treatment period

Inclusion criteria at randomization will be confirmed at Day 0. Adherence to all criteria listed in section 3.3 must be confirmed prior to randomization on Visit 4 (Day 0)

Patients confirmed to be eligible will be randomized at Day 0.

During the Day 0 visit, the patient should complete the following assessments: SGRQ and ACQ-6 completion, and then pre-BD spirometry 60 min and 30 min prior to IP administration.

Patients will be randomized to either placebo or benralizumab 30 mg every 4 weeks throughout the treatment period.

Patients will have more frequently scheduled visits in the 2 weeks after the first IP administration and then more infrequent visits for the rest of study duration (refer [Table 3](#)). Restrictions as set out in Section 3.9 will continue to apply throughout the treatment period. In case of an asthma worsening/exacerbation (see Section 4.1.4.1) patients should be evaluated at the study center when feasible.

At Visit 10 (Day 84±7), patients will come to the center for the End of Treatment (EOT) visit.

For patients who prematurely discontinued IP and are not willing to continue to participation in the study refer to Section 3.10 and 3.11.

Completion or early termination of the treatment will be registered via IWRS/IVRS for each patient.

4.3 Follow-up period

Patients who complete the double-blind randomized treatment period will have follow-up visit at Visit 11 (Day 112±7). For study assessments schedule during this visit please refer to [Table 3](#).

5. STUDY ASSESSMENTS

Medidata Rave Web Based Data Capture (WBDC) system will be used for data collection and query handling. The investigator will ensure that data are recorded on the electronic Case Report Forms as specified in the study protocol and in accordance with the instructions provided.

The investigator ensures the accuracy, completeness and timeliness of the data recorded and of the provision of answers to data queries according to the Clinical Study Agreement. The investigator will sign the completed electronic Case Report Forms. A copy of the completed electronic Case Report Forms will be archived at the study site.

5.1 Efficacy assessments

5.1.1 Spirometry

General requirements

Lung function (FEV₁ and forced vital capacity [FVC]) at the study center will be measured by spirometry using equipment provided by central vendor. Spirometry will be performed by the Investigator or authorized delegate according to American Thoracic Society/European Respiratory Society (ATS/ERS) guidelines ([Miller et al 2005](#)).

The central spirometry vendor is responsible for assuring that the spirometer meets ATS/ERS recommendations and that the study center personnel who will be performing the testing are properly certified. Spirometry calibration will be detailed in a separate spirometry procedures manual.

Important! Patients should withhold their SABA medication(s) for at least 6 hours prior to all scheduled lung function assessments. Twice daily LABA- or LAMA-containing therapies should be withheld for 12-24 hours and once daily LABA- or LAMA-containing therapies for >24 hours before spirometry. LTRA should be restricted for >24 hours and twice daily

theophyllines should be withheld for at least 12- 24 hours and once daily for >24 hours before spirometry assessments.

Options for handling patients who have inadvertently taken their asthma medication within the restricted window are described in Section 3.9.1.

Time of day for scheduled center visit spirometry

Spirometry testing should be done initiated in the morning between 6:00 AM and 11:00 AM according to the schedule provided in Table 2 and Table 3. All post-randomization spirometry assessments should be performed within ± 1.5 hours of the time at which the qualifying pre-BD FEV₁ spirometry was performed either at Visit 2 or Visit 3.

For example, if the spirometry (pre-BD FEV₁) was started at 08:00 AM at Visit 3 and this spirometry met inclusion #5, then all subsequent spirometry testing needs to be initiated between 06:30 AM and 9:30 AM.

Spirometry technique

Patients should avoid engaging in strenuous exertion for at least 30 minutes prior to spirometry measurements. Patients should avoid eating a large meal for at least 2 hours prior to spirometry measurements at the center. Forced expiratory maneuvers should be performed with the patient seated in an upright position. If this is not comfortable for the patient, standing is permitted. The same position should be used by the patient for each forced expiratory maneuver from enrolment throughout the study. The head must not be tilted during maneuvers and the thorax should be able to move freely; hence, tight clothing should be loosened. A nose-clip should be used for the maneuver. Mouthpieces of the same dimension and shape should be used by the patient from enrollment throughout the study.

The forced expiratory maneuver (FEV₁ and FVC) should start with a maximal inspiration and then followed by a fast and forceful expiration that should last for at least 6 seconds. It is important to encourage the patient to continue the expiration to be fast and forceful throughout the maneuver. Ensure that none of the following has occurred: coughing during the first second, glottis closure, leak or obstruction of the mouthpiece (by the tongue).

Multiple forced expiratory efforts (at least 3 but no more than 8) will be performed for each center spirometry session and the 2 best efforts that meet the ATS/ERS acceptability and reproducibility criteria will be recorded. The best efforts will be based on the highest FEV₁. The absolute measurement (for FEV₁ and FVC), and the percentage of predicted normal (PN) value (Quanjer et al 2012) will be recorded. The highest FVC will also be reported regardless of the effort in which it occurred (even if the effort did not result in the highest FEV₁).

Order of administration of usual asthma controller medication and IP relative to scheduled pre- and post-bronchodilator spiograms

The patient's usual morning asthma controller therapy must not be given until after the exhaled NO and pre-BD spirometry are complete.

For sites participating in the body plethysmography sub-study the usual asthma controller medication must be withheld till all the plethysmography assessments are completed. Investigational product dosing should also be not performed until pre-BD spirometry is complete.

Record keeping

A signed and dated copy of the pre- and post- BD printout must be kept at the study center for source data verification. The printout must be marked with the study code, patient enrolment code, date and time of measurement, and visit number.

Spirometry references

The Global Lung Function Initiative (GLI) equations will be used to determine the patients PN values and are pre-programmed into your spirometer ([Quanjer et al 2012](#)).

FEV₁ expressed as percent of the PN value will be calculated as follows:

[figure not shown]
$$FEV_1\% \text{ of PN} = FEV_1 \text{ measured} / FEV_{1PN} \times 100$$

5.1.1.1 Reversibility testing

The procedure described in this section refers to the reversibility testing that can be performed at either Visit 1, Visit 2 or Visit 3. If a patient is participating in the body plethysmography sub-study, reversibility testing can only be performed either at Visit 1 or Visit 2 only.

Bronchodilatation can be induced using albuterol (90 µg metered dose), salbutamol (100 µg metered dose) or levalbuterol (45 µg metered dose) up to a maximum of 4 inhalations). It is highly recommended to use a spacer device for this procedure. The algorithm for reversibility testing is outlined in [Figure 3](#).

Figure 3 Reversibility testing algorithm

1. Verify with the patient the medication restrictions to allow the reversibility assessment have been met (Section 3.8.1)
2. After a gentle and complete expiration, albuterol, salbutamol or levalbuterol is inhaled in one breath to TLC from a spacer device. The breath is then held for 5-10 seconds before the patient exhales. Four separate inhalations are delivered at approximately 30- second intervals. Post-BD spirometry should be performed 30 - 60 minutes later.
3. If the patient has not met reversibility criteria at Visit 1 further attempts to demonstrate reversibility are allowed at Visit 2 and Visit 3 for those patients participating in the main study. For those patients participating in the body plethysmography sub-study only one further attempt is allowed at Visit 2.

A lower total dose, eg, 2 inhalations instead of 4 puffs, can be used if there is a concern about any effect on the patient's heart rate, tremor, or safety.

The highest pre- and post-BD FEV₁ should be used to determine reversibility.

Reversibility is calculated as follows:

$$\% \text{ Reversibility} = \frac{(\text{post-BD FEV}_{1} - \text{pre BD FEV}_{1}) \times 100}{\text{pre-BD FEV}_{1}}$$

5.1.2 Fractional exhaled nitric oxide measurement

Airway inflammation will be evaluated using a standardized single-breath fractional exhaled nitric oxide (FeNO) test (ATS 2005).

Since spirometry can potentially impact the nitric oxide measurement, the FeNO test needs be completed prior to spirometry. In addition, subjects should not eat or drink 1 hour prior to having the FeNO, as this may affect the results.

While sitting, subjects are to inhale to total lung capacity through the NIOX MINO® Airway Inflammation Monitor (Aerocrine, New Providence, New Jersey) and then exhale for 10 seconds at 50 mL/sec (assisted by visual and auditory cues). The value obtained will be recorded and the process repeated twice for a total of 3 measurements. The 3 measurements will be printed to serve as a source document.

NIOX MINO® sensors will be replaced as recommended by the manufacturer.

5.2 Safety assessments

5.2.1 Laboratory safety assessments

Safety laboratory tests (list provided in Table 4 below) will be performed in a central laboratory. For information on methods of collection, assessment, labelling, storage, and shipment of samples please refer to the separate Laboratory Manual. Safety samples will be collected in accordance with the schedules provided in Table 2 and Table 3.

Hematology and urinalysis will be assessed in line with the schedules provided in Table 2 and Table 3.

The following laboratory variables will be measured:

Table 4 Laboratory safety variables

Hematology/hemostasis (whole blood)	Clinical chemistry (serum or plasma)	Urinalysis
Hematocrit	Alkaline phosphatase (ALP)	Appearance
Hemoglobin (Hb)	Aspartate transaminase (AST)	Blood
Mean corpuscular volume (MCV)	Alanine transaminase (ALT)	Color
Platelet count	Blood urea nitrogen (BUN)	Ketones
Red blood cell (RBC)	Calcium	Microscopy including WBC/high power field (HPF), RBC/HPF
White blood cell (WBC) count with differential	Chloride	pH
	Creatinine	Specific gravity
	Gamma-GT (gamma-glutamyl transpeptidase)	
	Glucose	
	Phosphorus	
	Potassium	
	Sodium	
	Bilirubin, total	
	Cholesterol, total	
	Uric acid	

a Eosinophils, basophils and monocytes counts will be redacted from central laboratory reports except for Visit 1 (see Section 3.7).

The Investigator should make an assessment of the available results with regard to clinically relevant abnormalities. The laboratory results should be signed and dated and retained at centre as source data for laboratory variables. For information on how AEs based on laboratory tests should be recorded and reported, see Section 6.3.

NB. In case a subject shows an AST **or** ALT $\geq 3 \times \text{ULN}$ **and** total bilirubin $\geq 2 \times \text{ULN}$ please refer to [Appendix D](#) ‘Actions Required in Cases of Increases in Liver Biochemistry and Evaluation of Hy’s Law’, for further instructions.

5.2.1.1 Pregnancy test

The following tests are applicable to female patients only and will be conducted in accordance with the schedules provided in [Table 2](#) and [Table 3](#).

- Serum beta-hCG: To be done at screening Visit 1, Visit 10 and premature IP discontinuation visit (IPD), for WOCBP (analyzed at central laboratory)
- FSH: To be done at screening Visit 1 only, for female patients to confirm postmenopausal status in women <50 years who have been amenorrheic for ≥ 12 months
- Urine HCG: To be performed at the study center for WOCBP at each treatment visit (before IP administration on Visit 4, Visit 8, Visit 9, Visit 10, IPD and Visit 11) using a dipstick. A positive urine test result must be confirmed with serum beta HCG.

5.2.2 Physical examination

Physical examination will be done in accordance with the schedules provided in [Table 2](#) and [Table 3](#).

Baseline data will be collected at Visit 1. Any new finding(s) or aggravated existing finding(s), judged as clinically significant by the Investigator, will be reported as an AE as described in Section [6.3](#).

5.2.2.1 Complete physical examination

A complete physical examination will be performed and include an assessment of the following: general appearance, respiratory, cardiovascular, abdomen skin, head and neck (including ears, eyes, nose and throat), lymph nodes, thyroid, abdomen, musculo-skeletal (including spine and extremities) and neurological systems.

5.2.2.2 Brief physical examination

The brief physical examination includes an assessment of the general appearance, abdomen, cardiovascular, and respiratory system. For the brief physical examination only information on whether the assessment was performed or not is to be recorded.

5.2.3 Electrocardiogram

5.2.3.1 Resting 12-lead electrocardiogram

Electrocardiograms (ECG) are to be performed in accordance with the schedule provided in [Table 2](#) and [Table 3](#).

A 12-lead ECG will be taken in supine position, after the patient has been resting for at least 5 minutes. The assessment should be performed before interventions with the patient (eg, spirometry and administration of the asthma-related medications and IP).

The Investigator or authorized delegate will be responsible for the overall interpretation and determination of clinical significance of any potential ECG findings. In case of discrepancy between the Investigators interpretation and that provided by the ECG machine (if applicable), the Investigator's interpretation takes precedence and should be noted on the printout and recorded in the eCRF. Two identical copies of the ECG will be produced, quality checked,

and kept in case of further need for re-evaluation. The ECG printouts will be signed and dated by the Investigator and stored at the study center.

ECG data and evaluation will be recorded in the eCRF.

5.2.4 Vital signs

5.2.4.1 Pulse and blood pressure

Pre-dose vital signs (pulse, blood pressure, respiration rate, and body temperature) are to be obtained in accordance with schedule provided in [Table 2](#) and [Table 3](#)

Vital signs are to be taken prior to IP administration, and, if possible, before blood drawing and usual asthma controller medication. Vital signs should also be taken prior to bronchodilator administration if applicable for that visit.

5.2.4.2 Body temperature

Body temperature is to be recorded in degrees Celsius.

5.3 Other assessments

5.3.1 Weight and height

Weight and height will be measured, and BMI calculated in accordance with schedules provided in [Table 2](#).

The patient's weight will be recorded in kilograms; height will be recorded in centimeters.

Weight and height measurements will be performed in light clothing and with shoes off.

5.3.2 Patient reported outcomes

Patients will complete patient-reported outcome (PRO) assessments using a tablet ePRO device at the site. Patients will complete a training module prior to the first assessment to ensure that they understand how to use the device.

PRO assessments should be done before other visit procedures.

5.3.2.1 Asthma Control Questionnaire

The ACQ-6 is a shortened version of the Asthma Control Questionnaire (ACQ) that assesses asthma symptoms (nighttime waking, symptoms on waking, activity limitation, shortness of breath, wheezing, and short-acting β_2 agonist use) omitting the FEV₁ measurement from the original ACQ score.

Patients are asked to recall how their asthma has been during the previous week by responding to 1 bronchodilator use question and 5 symptom questions.

Questions are weighted equally and scored from 0 (totally controlled) to 6 (severely uncontrolled). The mean ACQ-6 score is the mean of the responses. Mean scores of ≤ 0.75

indicate well-controlled asthma, scores between 0.75 and ≤ 1.5 indicate partly controlled asthma, and a score > 1.5 indicates not well controlled asthma (Juniper et al 2006). Individual changes of at least 0.5 are considered to be clinically meaningful.

By omitting the ACQ-6 bronchodilator use question from the scoring algorithm, an ACQ-5 score can be calculated.

The questionnaire will be completed at the study center via provided site tablet (ePRO) in accordance with schedule provided in [Table 2](#) and [Table 3](#)

5.3.2.2 St. George's Respiratory Questionnaire

The St. George's Respiratory Questionnaire (SGRQ) is a 50-item PRO instrument developed to measure the health status of subjects with airway obstruction diseases (Jones et al 1991). The questionnaire is divided into 2 parts: part 1 consists of 8 items pertaining to the severity of respiratory symptoms in the preceding 4 weeks; part 2 consists of 42 items related to the daily activity and psychosocial impacts of the individual's respiratory condition. The SGRQ yields a total score and 3 domain scores (symptoms, activity, and impacts). The total score indicates the impact of disease on overall health status. This total score is expressed as a percentage of overall impairment, in which 100 represents the worst possible health status and 0 indicates the best possible health status. Likewise, the domain scores range from 0 to 100, with higher scores indicative of greater impairment. Specific details on the scoring algorithms are provided by the developer in a user manual (Jones et al 2009).

5.3.2.3 Patient Global Impression of Severity assessments

The Patient Global Impression of Severity (PGI-S) is a single item designed to capture the patient's perception of overall symptom severity at the time of completion using a 6-point categorical response scale (no symptoms to very severe symptoms). For the time of completion, refer to [Table 3](#).

The PGI-S should be completed on the site tablet by the patient before other study assessments and IP administration per the schedule provided in [Table 3](#)

5.3.2.4 Clinician and Patient Global Impression of Change assessments

Clinician Global Impression of Change (CGI-C) and Patient Global Impression of Change (PGI-C) instruments are used for an overall evaluation of response to treatment. The Investigator (clinician) and the patient will be asked to rate the degree of change in the overall asthma status compared to the start of treatment, ie, randomization visit. A 7-point rating scale will be used: 1= Very Much Improved; 2= Much Improved; 3= Minimally Improved; 4= No Changes; 5=Minimally Worse; 6=Much Worse and 7= Very Much Worse.

The CGI-C and PGI-C should be completed on the site tablet by the patient before other study assessments and IP administration per the schedule provided in [Table 3](#)

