2.4 Other objectives for the main study

Other objectives:	Outcome measure
To evaluate patient impression of overall asthma severity (PGI-S) and overall change from baseline as reported by the patient (PGI-C) and clinician (CGI-C)	
 • Change from baseline (Visit 4) in PGI-S at all post-baseline assessment timepoints • Clinician-reported global change in asthma from baseline (Visit 4) as measured by CGI-C • Patient-reported global change in asthma from baseline (Visit 4) as measured by PGI-C

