8.4.1.8 Patient and Clinician Global Impression of Change

Clinician Global Impression of Change (CGI-C) and Patient Global Impression of Change (PGI-C) instruments are used for an overall evaluation of response to treatment. The Investigator (clinician) and the patient will be asked to rate the degree of change in the overall asthma status compared to the start of treatment, ie, randomization visit. A 7-point rating

scale will be used: 1=Very Much Improved; 2=Much Improved; 3=Minimally Improved; 4=No Changes; 5=Minimally Worse; 6=Much Worse and 7=Very Much Worse.

The clinician and patient will be asked, separately, to rate the degree of change in the overall asthma status compared to the randomization visit. Calculation of percentages will be based on the number of subjects in the full analysis set with a completed assessment. There will be no imputation for missing values.

Patients will also be categorized according to the following responses post-baseline, separately for both the CGI-C and PGI-C:

- Very much improved, much improved, minimally improved → Improved
- Very much improved, much improved → Much improved
- Very much improved → Very much improved

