#### **3.3.2 Clinician Global Impression of Change and Patient Global Impression of Change**

Clinician Global Impression of Change (CGI-C) and Patient Global Impression of Change (PGI-C) instruments are used for an overall evaluation of response to treatment. The Investigator (clinician) and the patient will be asked to rate the degree of change in the overall asthma status compared to the start of treatment, ie, randomization visit. A 7-point rating scale will be used: 1=Very Much Improved, 2=Much Improved, 3=Minimally Improved, 4=No Changes, 5=Minimally Worse, 6=Much Worse, and 7=Very Much Worse.

The Investigator and the patient will be asked to rate the degree of change in the overall status compared with the randomization visit. There will be no imputation for missing values.

Patients will also be categorized according to the following responses post-baseline, separately for CGI-C and PGI-C:

- Very much improved, much improved, minimally improved → ‘Improved’
- Very much improved, much improved → ‘Much improved’
- Very much improved → ‘Very much improved’

Agreement between CGI-C and PGI-C will be assessed at each visit, where agreement is achieved when both the Investigator and the patient provide the same response (eg, if both the Investigator and the patient indicate a response of 1 (very much improved) at a particular visit, agreement is achieved for that visit). Agreement will also be assessed for categorized responses at each visit.

A responder will be defined for CGI-C and PGI-C separately as anyone with a response of Improved, Much improved, or Very much improved at the EOT visit.

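### One sentence in Protocol 5.3.2.4 has the patient complete the clinician's scale (CGI-C), contradicting every other statement of who rates it; the exploratory CGI-C results depend on sites not following it literally

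*Protocol*

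**What the plan says.** Protocol 5.3.2.4 first describes two raters using the same seven-point scale: "The Investigator (clinician) and the patient will be asked to rate the degree of change in the overall asthma status". It then tells sites how the scales are to be completed: "The CGI-C and PGI-C should be completed on the site tablet by the patient before other study assessments and IP administration".

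Elsewhere the rater of CGI-C is clear. Protocol 2.4 defines the outcome as "Clinician-reported global change in asthma from baseline (Visit 4) as measured by CGI-C", and the synopsis and SAP 1.1.4 say the same. Protocol 8.4.1.8 states: "The clinician and patient will be asked, separately, to rate the degree of change in the overall asthma status". SAP 3.3.2 states: "The Investigator and the patient will be asked to rate the degree of change in the overall status compared with the randomization visit".

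Two planned outputs need CGI-C to come from the clinician. SAP 3.3.2 says "Agreement between CGI-C and PGI-C will be assessed at each visit", and counts a visit as agreeing under this rule: "agreement is achieved when both the Investigator and the patient provide the same response". SAP 4.2.7.2 tabulates that agreement as counts and percentages by group and visit. It also fits a logistic regression on treatment and region to CGI-C responders at the end-of-treatment visit.

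**The concern.** The closing sentence of 5.3.2.4 is the only place in that section that tells a site who enters the scales, on what device and at what point in the visit. It is an operating instruction. Its setting supports the wrong reading: 5.3.2.4 sits under 5.3.2, which covers patient-reported outcomes and describes patients filling in questionnaires on the site tablet. A site that loaded both items into the patient's tablet session would be following the sentence as written.

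At such a site the study would hold two patient ratings, one of them labelled as the clinician's. CGI-C is the only clinician-rated global measure among the listed outcomes, so nothing else would supply the missing view. Agreement between the two ratings could be read as clinicians confirming what patients reported when no clinician had rated.

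**Working it through.** The plan gives no figure to reproduce, because the question is who rates. The check sets every statement on that question side by side.

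1. Synopsis, Protocol 2.4 and SAP 1.1.4 (objectives): CGI-C is clinician-reported, PGI-C is patient-reported.
2. Protocol Table 3, block heading: the block covers both patient- and clinician-reported outcomes.
3. Protocol 5.3.2.4, first paragraph: the Investigator and the patient each rate.
4. Protocol 5.3.2.4, last sentence: the patient completes both.
5. Protocol 8.4.1.8: "The clinician and patient will be asked, separately, to rate the degree of change".
6. SAP 3.3.2: the Investigator and the patient are the two raters, and agreement means that both gave the same response.

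Item 4 stands alone against the other five. The likely origin is Protocol 5.3.2.3, where nearly the same sentence is used for PGI-S, a scale the patient does complete. That is an inference from the wording.

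Next, what the two CGI-C outputs would contain if item 4 were followed. Let *s* be the share of CGI-C records entered by the patient, *A* the true clinician-patient agreement, and *B* the proportion of visits at which a patient gives the same answer to both items. Taking *A* to be the same at all sites, the tabulated agreement is

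(1 − *s*) × *A* + *s* × *B*.

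- At *s* = 0 this is *A*, the quantity the SAP wants.
- At *s* = 1 it is *B*, which measures a patient's consistency with himself or herself and says nothing about the clinician.
- *B* is probably high, since the same question is put twice on the same scale in one session, but the documents give no value for *A*, *B* or *s*.

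The logistic regression uses one CGI-C rating per patient, at end of treatment. Patient-entered records would make it largely repeat the PGI-C analysis. The sentence applies to both arms alike in a double-blind trial, so the treatment comparison would not be biased for that reason. It would be a comparison of patient ratings carrying the wrong label.

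Last, whether the error could be caught afterwards. Neither document describes a rater identifier, a separate clinician log-in, or a rule for records attributed to the wrong rater.

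**The case against.** The best reply is that the documents largely settle the matter. The paragraph immediately above the faulty sentence names the Investigator, the objectives call the scale clinician-reported, and Protocol 9.1 provides for site training on the electronic questionnaires. A careful site would probably have the clinician rate. This stands, and it is why the consequence is stated only for sites that follow the sentence literally. It does not remove the contradiction, because 9.1 does not say who enters CGI-C.

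It is also fair to say that these are exploratory outcomes with nominal p-values (SAP 1.1.4 and 4.1). That stands too and limits the weight of the point.

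A reader might infer more than the documents support:

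- *That nothing keeps the ratings independent.* Protocol 8.4.1.8 says the two are asked separately. What is missing is operational detail on order and on keeping each answer from the other rater.
- *That clinicians rate after seeing PGI-C.* Nothing places CGI-C after PGI-C, and 5.3.2.4 puts both at the start of the visit. Nothing says patient answers are shown to the Investigator.
- *That the clinician should also be kept from PGI-S and ACQ-6.* No text requires a clinician's global impression to be formed without symptom information. That would be a preference.
- *That Table 3 schedules CGI-C at a visit without PGI-C, so agreement fails there.* The copy of the table read here is damaged. Its dosing marks do not line up with Days 0, 28 and 56, and its urine pregnancy row shows five marks where 5.2.1.1 lists six visits. No visit count is drawn from it. A visit lacking one rating would in any case simply yield no pair.

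**Conclusion.** The contradiction is real and confined to one sentence. If a site follows it literally, that site's CGI-C data are patient ratings, and both the CGI-C responder analysis and the agreement table misdescribe them. The share of centres affected could lie anywhere from none to all, and the documents give no basis for narrowing that. The unconditional reading, that CGI-C and the agreement table will fail to measure what they claim, is not supported: it would require sites to disregard the rest of 5.3.2.4 and the objectives. Agreement is tabulated and not tested, so no inferential claim rests on it. The primary FEV1 analysis, the secondary analyses and PGI-C itself are unaffected. The correction is worth making because it costs almost nothing and because a clinician's impression not recorded at the visit cannot be recovered later.

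**What to change.** Replace the closing sentence of Protocol 5.3.2.4 with wording to this effect: *The patient completes PGI-C and the Investigator completes CGI-C, separately and each without seeing the other's answer at that visit. Both are completed ahead of the visit's remaining assessments and any dosing, as scheduled in Table 3.* This puts the word separately, already in 8.4.1.8, into practice.

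Add one line to SAP 3.3.2 or 4.2.7.2: a CGI-C record found to have been entered by the patient is left out of both the agreement table and the CGI-C responder analysis. Under the existing rule in SAP 3.3.2 it would not be imputed. Since no rater identifier is described, finding such records would depend on site or device records. If ratings have already been collected, the question can be put to sites during the deviation review before database lock (SAP 2.2.1).

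The cost is one protocol sentence, a matching site instruction and one SAP line. No visit, procedure or staff is added.
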